4.2. Exclusion Criteria

Any potential subject who meets any of the following criteria will be excluded from participating in the study:

1. Hospitalized subjects or subjects expected to be hospitalized within 24 hours of screening.

Note: Any stay in the emergency room or in the observational unit of at least 24 hours will be considered hospitalization for the purposes of the study.

2. History of or concurrent illness (beyond a comorbid condition) that in the opinion of the investigator, might confound the results of the study or pose an additional risk in administering study drug to the subject or that could prevent, limit, or confound the protocol-specified assessments.

3. Subjects who had major surgery within the 28 days prior to randomization or have planned major surgery through the course of the study.
4. Subjects who are considered by the investigator to be immunocompromised within the past 12 months, whether due to underlying medical condition (eg, malignancy or genetic disorder other than immunoglobulin A deficiency, or human immunodeficiency virus [HIV] infection) or medical therapy (eg, medications other than corticosteroids for the treatment of COPD or asthma exacerbations, chemotherapy, radiation, stem cell or solid organ transplant).
5. Subject has known or suspected chronic or acute hepatitis B or C infection.
6. Subject has known allergies, hypersensitivity, or intolerance to JNJ-53718678 or to any of the excipients of the JNJ-53718678 or placebo formulation (refer to the IB¹⁵).
7. Subject with current or planned participation in another clinical study where study drug/investigational device is being administered while participating in the current study.
8. Subjects unwilling to undergo mid-turbinate nasal swab procedures or with any physical abnormality which limits the ability to collect regular nasal specimens.
9. Subjects unable to take medications orally or with a known gastrointestinal-related condition that is considered by the sponsor or investigator to be likely to interfere with study drug ingestion or absorption.
10. Women who are pregnant or breastfeeding.
11. Men who plan to father a child while enrolled in this study or within 90 days after the last dose of study drug.
12. Subject with clinically significant abnormal ECG findings (other than QTcF interval >500 ms, see exclusion criterion 13) not consistent with the underlying condition in the study population, as judged by the investigator.
13. Confirmed QTcF interval >500 ms per the machine read parameter result at screening. Confirmation needs to be obtained by repeat triplicate ECG recording prior to dosing.
14. Subjects who are using any disallowed medication as listed in Section 8.
15. Subjects with history of drug or alcohol abuse according to Diagnostic and Statistical Manual of Mental Disorders (5th edition) criteria within 1 year before screening.
16. Subjects who received an investigational vaccine at any time prior to the study, or an investigational drug, or used an invasive investigational medical device within 30 days or 5 elimination half-lives (whichever is longer) prior to screening or is currently

enrolled in an investigational study.

17. Subject is a family member of the employees of the investigator or study-site with direct involvement in the proposed study or other studies under the direction of that investigator or study-site or of the investigator.

Note: Investigators should ensure that all study enrollment criteria have been met at screening. If a subject's clinical status changes (including any available laboratory results or receipt of additional medical records) after screening but before the first dose of study drug is given such that he or she no longer meets all eligibility criteria, then the subject should be excluded from participation in the study.

4.3. Prohibitions and Restrictions

Potential subjects must be willing and able to adhere to the following prohibitions and restrictions during the course of the study to be eligible for participation:

1. Agree to follow all requirements that must be met during the study as noted in the inclusion and exclusion criteria (eg, contraceptive requirements).
2. Agree to the daily completion of the patient-reported outcomes, additional questions, study medication and concomitant medication log, swabbing log, and temperature log.
3. Concurrent administration of medications/use of licensed devices is allowed as supportive therapy per local standard of care, as long as the medication/licensed device will not affect the subject's participation in the study and is in accordance with allowed concomitant therapy.

Refer to Section 8 for details regarding prohibited and restricted therapy during the study.

5. TREATMENT ALLOCATION AND BLINDING

Treatment Allocation

Procedures for Randomization and Stratification

Central randomization will be implemented in this study. Subjects will be randomly assigned to 1 of 3 treatments (Treatments A to C; 1:1:1 randomization). Randomization will be based on a computer-generated randomization schedule prepared before the study by or under the supervision of the sponsor. The randomization will be balanced by using randomly permuted blocks and will be stratified by time since symptom onset at randomization (≤ 3 days and > 3 days). The interactive web response system (IWRS) will assign a unique treatment code, which will dictate the treatment assignment and matching study drug kits for the subject. The requestor must use his or her own user identification and personal identification number when contacting the IWRS, and will then give the relevant subject details to uniquely identify the subject.

Blinding

The investigator will not be provided with randomization codes. The codes will be maintained within the IWRS, which has the functionality to allow the investigator to break the blind for an individual subject.

In general, randomization codes will be disclosed fully only if the study is completed and the clinical database is closed. However, if an interim analysis is specified, the randomization codes and, if required, the translation of randomization codes into treatment and control groups will be disclosed to those authorized and only for those subjects included in the interim analysis. Otherwise, the blind should be broken only if specific emergency treatment/course of action would be dictated by knowing the treatment status of the subject. In such cases, the investigator may in an emergency determine the identity of the treatment by contacting the IWRS. It is recommended that the investigator contacts the sponsor or its designee, if possible, to discuss the particular situation, before breaking the blind. Telephone contact with the sponsor or its designee will be available 24 hours per day, 7 days per week. In the event the blind is broken, the sponsor must be informed as soon as possible. The date and reason for the unblinding must be documented in the appropriate section of the electronic case report form (eCRF). The documentation received from the IWRS indicating the code break is filed in the Trial Master File.

6. DOSAGE AND ADMINISTRATION

The subjects will receive the treatments as described in [Table 2](#). Study drugs will be administered orally.

Table 2: Treatment Overview

Treatment	Dosing Regimen	Volume and Formulation
A	500 mg JNJ-53718678 once daily for 7 days	8 mL + 42 mL oral solution of JNJ-53718678 ^a
B	80 mg JNJ-53718678 + matching placebo once daily for 7 days	8 mL oral solution of JNJ-53718678 ^a + 42 mL of matching placebo solution
C	placebo once daily for 7 days	8 mL + 42 mL matching placebo solution

^a JNJ-53718678 is formulated as an oral solution containing 10 mg/mL of active drug substance (G024). The matching placebo consists of the oral vehicle solution without active drug substance (G026).

Study drug administration should start as soon as possible, but no later than 4 hours after randomization, which should occur within a maximum of 5 days after RSV symptom onset. Study drug administration should occur once daily at approximately the same time each day. JNJ-53718678/placebo can be administered without regard to meals and is preferably followed by drinking a glass of water. Each dosing day, the same total volume of study drug solution should be administered, ie, 50 mL, divided over 2 separate but sequential intakes (1 container with 8 mL and 1 container with 42 mL).

On Day 1, date and time of dosing will be captured by the site staff in the eCRF. At home, date and time of dosing will be captured in the study medication log, to be completed by the subject in the electronic device. On Day 3 and Day 8 (days with pharmacokinetic sampling), the time of the meal, if any within 2 hours before or after dosing, will also be recorded in the study medication log.

Study-site personnel will instruct subjects on how to store study drug for at home use as indicated for this protocol.

7. TREATMENT COMPLIANCE

On Day 1, study drug will be administered orally at the study site.

In case of vomiting, the subject should not be redosed.

In case a dose was missed, the dose should be given as soon as possible but within 12 hours after the scheduled time. If more than 12 hours have elapsed, the dose should be skipped and the next dose should be given at the next scheduled time point per the initial dosing schedule.

8. CONCOMITANT THERAPY

Concomitant medications, except those listed below, are allowed during this study. All concomitant medications and supportive therapy are to be recorded in the eCRF, as well as in the source documents, from the date the ICF is signed through to the end of study visit. The dosage, route of administration, frequency, start and stop dates, and the indication should be noted in the source documentation and the eCRF.

Subjects will be required to document use of concomitant medication in the electronic medication log from signing of the ICF until the last study visit, which will serve as source document for the site staff to complete the eCRF.

Subjects can receive medications such as acetaminophen/paracetamol, non-steroidal anti-inflammatory drugs, or antihistamines, taking into account their respective package insert, at the investigator's discretion.

Prescription medications intended to treat the symptoms/sequelae of the RSV infection are permitted, including:

- Inhaled β -agonists or anticholinergics (also permitted as maintenance therapy for the underlying asthma or COPD);
- Inhaled corticosteroids and, to a certain extent, systemic corticosteroids (see below);
- Oral/intravenous/intramuscular antibiotics such as β -lactams and azithromycin.

Note: The temporary use of over-the-counter medications in the 14 days prior to randomization is permitted. The use of vitamins and mineral supplements is also permitted.

The following therapies are not permitted during the study and for the time period prior to screening as noted:

- Herbal supplements with active metabolic enzyme inducing components (eg, St-John's Wort) within 21 days prior to randomization and during the study with the exception of topically administered products;
- The following prescription medications:

- Macrolide antibiotics (with the exception of azithromycin).
- Systemic corticosteroids if used for >7 consecutive days immediately prior to randomization at doses higher than 20 mg/day of prednisone or equivalent. Subjects meeting the eligibility criteria at screening but requiring increased doses of systemic corticosteroids (>20 mg/day of prednisone or equivalent) for a prolonged period (>7 consecutive days) during the study are allowed to continue participating in the study.
- Prescription medications used within 14 days prior to randomization and during the study with an antiviral effect on RSV to treat the RSV infection itself (eg, inhaled/oral ribavirin, intravenous RSV immunoglobulin). Prescription medications intended to treat the symptoms/sequelae of the RSV infection are permitted.
- Prescription medications which are known to be a strong inducer or a strong inhibitor of CYP3A4 enzymes, such as, but not limited to, erythromycin, clarithromycin, ritonavir, and rifampin, within 14 days prior to screening and during the study or CYP3A substrates with narrow therapeutic index such as, but not limited to, anti-arrhythmics (amiodarone, disopyramide, flecainide, mexiletine, systemic lidocaine, propafenone, quinidine), antihistamines (astemizole, terfenadine), or gastrointestinal/gastroesophageal reflux disease drugs (cisapride).
- Any other investigational drug within 30 days or 5 elimination half-lives of that drug (whichever is longer) prior to screening and during the study;
- Any investigational vaccine, including investigational RSV vaccines, at any time prior to and during the study;
- JNJ-53718678 prior to screening.

9. STUDY EVALUATIONS

9.1. Study Procedures

9.1.1. Overview

The [TIME AND EVENTS SCHEDULE](#) summarizes the frequency and timing of antiviral effect, clinical course, safety, pharmacokinetic, biomarker, and MRU assessments applicable to this study.

If multiple assessments are scheduled for the same time point, it is recommended that procedures be performed in the following sequence: ECG, vital signs, clinical parameters, blood sampling, and physical examination. Actual dates and times of assessments will be recorded in the source documentation and CRF.

Medical resource utilization data will be collected. Refer to Section [9.6](#), for details.

The maximum amount of blood drawn from each subject for study-specific purposes will not exceed 450 mL over the duration of the study.

Repeat or unscheduled samples may be taken for safety reasons or for technical issues with the samples.

Assessments which should be performed around the dosing time point as per the [TIME AND EVENTS SCHEDULE](#) should be done prior to actual dosing on Day 1 and preferably prior to dosing on the other days.

9.1.2. Screening Phase

The procedures specified in the [TIME AND EVENTS SCHEDULE](#) will only be performed after written informed consent has been obtained.

Screening will be completed and randomization will be performed within a maximum of 5 days after the onset of RSV symptoms to ensure the eligibility of the subject. Procedures that are standard of care and performed within approximately 48 hours prior to randomization may be used in determining study eligibility.

Blood samples for serum chemistry and hematology and a urine sample for urinalysis will be collected at screening and analyzed at the central laboratory. Subjects can start treatment before the laboratory results are available. In case abnormalities as described in Section 10.2 are observed in the blood samples collected at screening after the subject has started treatment, treatment may need to be discontinued.

During screening, one mid-turbinate nasal swab will be collected for:

- RSV diagnosis using a rapid PCR-based (preferably locally available) or rapid-antigen-detection test. In case the test detects more than one virus, the subject is eligible as long as RSV is one of the viruses detected.
- RSV diagnosis confirmation using a PCR-based assay post-hoc (at the central laboratory).
- Examination for the presence of other viruses or bacteria using multiplex PCR post-hoc (at the central laboratory).

Note: Leftover samples will be stored for biomarker research if warranted.

A clinical evaluation will be performed. This includes but is not limited to respiratory rate, heart rate, SpO₂, and body temperature (measured by the same method and preferably by the same person throughout the study). In addition, to evaluate RSV symptoms' presence and severity, subjects will have to complete the RI-PRO, answer the additional questions about health and functioning, and subjects enrolled after approval of this amendment will also have to complete the RiiQ Symptom Scale. Subjects will have to rate their HRQOL by completing the 5-level EuroQol 5-Dimension (EQ-5D-5L), and subjects enrolled after approval of this amendment will also have to complete the RiiQ Impact Scale.

9.1.3. Double-Blind Treatment Phase

Assessments to be performed during the treatment phase are specified in the [TIME AND EVENTS SCHEDULE](#).

Day 1/Day of Randomization

Eligible subjects will be randomized on Day 1. Study drug administration should start as soon as possible, but no later than 4 hours after randomization, which should occur within a maximum of 5 days after RSV symptom onset. Subjects will receive the first dose of study drug on Day 1 at the healthcare facility. Date and time of dosing will be captured by the site staff in the eCRF.

Assessments to be performed on Day 1 are specified in the [TIME AND EVENTS SCHEDULE](#).

Day 2 to Day 8 (End of Treatment)

Study drug administration continues until 7 doses have been taken. Subjects will receive 7 doses in total without regard to meals, administered once daily preferably at approximately the same time as on Day 1 each day. Study drug administration is preferably followed by drinking a glass of water. On Day 1, study-site personnel can dispense to the subject all the required study drug for dosing at home, but partial dispensing at other visits is also allowed. Study-site personnel will instruct subjects on how to use and store study drug for at home dosing. Date and time of dosing will be captured in the study medication log, to be completed by the subject in the electronic device.

Assessments will be performed as detailed in the [TIME AND EVENTS SCHEDULE](#).

Telephone calls to the subjects to facilitate compliance with study procedures between outpatient study visits are permitted.

9.1.4. Posttreatment Phase (Follow-Up)

Day 9 to Day 28(±3)

Subjects will be evaluated for a total of 28 days post randomization. Subjects will be required to return to the healthcare facility as an outpatient or, if feasible, have a home visit scheduled, for follow-up assessments on Day 14 and Day 21 as indicated in the [TIME AND EVENTS SCHEDULE](#). On Day 28, subjects will be contacted by site staff for a telephone follow-up visit. In case subjects are experiencing ongoing AEs or have clinically significant laboratory abnormalities at time of the Day 21 follow-up visit, subjects might be requested, at the discretion of the investigator, to have a safety follow-up visit at the site or, if feasible, at home on Day 28. On Day 28 all subjects will complete the study. Assessments will be performed as indicated in the [TIME AND EVENTS SCHEDULE](#).

Subjects who prematurely discontinue study drug treatment for any reason (except withdrawal of consent) will be asked to continue with their remaining study visits and assessment schedule, or, at a minimum, to return to the site for a Withdrawal and a Safety Follow-up Visit. Subjects who withdraw consent during the treatment or follow-up phase will be offered and be encouraged to attend an optional Safety Follow-up Visit. At the Withdrawal and Safety Follow-up Visits, the same assessments as on the Day 8 and Day 21 visits, respectively, will be performed. Assessments will be performed as indicated in the [TIME AND EVENTS SCHEDULE](#).

9.2. Efficacy Evaluations

9.2.1. Antiviral Activity

As an evaluation of antiviral activity, the RSV viral load in nasal secretions, obtained via mid-turbinate nasal swab, will be measured at the central lab using a qRT-PCR assay. Mid-turbinate swab specimens for the determination of RSV viral load will be collected at several time points during the study as indicated in the [TIME AND EVENTS SCHEDULE](#). Mid-turbinate swabs should be collected from the same nostril throughout the study (unless precluded due to bleeding). It will be collected in the eCRF or the electronic device (for home swabs) which nostril was sampled.

The first mid-turbinate nasal swab should be collected as close as possible and prior to the first administration of study drug (on Day 1). The next swabs (from Day 2 to Day 8) should be collected preferably at approximately the same time as on Day 1 each day. On Day 8, the investigator will check whether the subject is still symptomatic. For asymptomatic subjects swabbing will be stopped. For subjects still symptomatic, swabbing will be continued daily until the subject becomes asymptomatic or until Day 13 at the latest. Whether a subject is still symptomatic will be checked with daily telephone calls between the subject and site staff (and/or by review of the transmitted ePRO data) in case swabbing is performed by the subject (or his/her spouse, partner, relative, or other caregiver) or by an HCP other than investigational site staff. On Day 14 and Day 21, a swab will be collected during the scheduled visit. During scheduled visits on Day 1, Day 3, Day 8, Day 14, and Day 21, swabs must be collected by an HCP (investigator/study-site personnel). On the other days, mid-turbinate swabs are collected at home preferably by an HCP and, only if not possible by an HCP, by the subject (or his/her spouse, partner, relative, or other caregiver) after being properly trained by the investigator/study-site personnel. In case preferred by the subject, all mid-turbinate swabbing may also be performed at the site.

The sampling should be documented in the electronic device or the eCRF (for the sampling at the scheduled visits).

Additional information about the collection, handling, and shipment of biologic samples can be found in the laboratory manual.

Changes in viral load will be evaluated but will not be reported as AEs.

If feasible, the RSV infectious virus titers as measured by quantitative culture of RSV (plaque assay) on selected nasal swab samples, may also be assessed.

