- q. Mid-turbinate nasal swabs will be taken to assess RSV viral load and emergence of mutations in the viral genome potentially associated with resistance to JNJ-53718678. The RSV infectious virus titers as measured by quantitative culture of RSV (plaque assay) may be assessed on selected nasal swab samples (pending feasibility of performing such an assay). Mid-turbinate swabs should be collected from the same nostril throughout the study (unless precluded due to bleeding). The first mid-turbinate nasal swab should be collected as close as possible and prior to the first administration of study drug (on Day 1). The next swabs (from Day 2 to Day 8) should be collected preferably at approximately the same time as on Day 1 each day. On Day 8, the investigator will check whether the subject is still symptomatic. For asymptomatic subjects swabbing will be stopped. For subjects still symptomatic, swabbing will be continued daily until the subject becomes asymptomatic or until Day 13 at the latest. Whether a subject is still symptomatic will be checked with daily telephone calls between the subject and site staff (and/or by review of the transmitted electronic patient-reported outcome [ePRO] data) in case swabbing is performed by the subject (or his/her spouse, partner, relative, or other caregiver) or by an HCP other than investigational site staff. On Day 14 and Day 21, a swab will be collected during the scheduled visit. During scheduled visits on Day 1, Day 3, Day 8, Day 14, and Day 21, swabs must be collected by a healthcare professional (HCP) (investigator/study-site personnel). On the other days, mid-turbinate swabs are collected at home preferably by an HCP and, only if not possible by an HCP, by the subject (or his/her spouse, partner, relative, or other caregiver) after being properly trained by the investigator/study-site personnel. In case preferred by the subject, all mid-turbinate swabbing may also be performed at the site. Date and time of swabs collected at home need to be recorded on the electronic device in a swabbing log. All subjects will be given appropriate mid-turbinate nasal swabs and Universal Transport Medium (same supplies as those used to collect nasal samples at the sites) to collect mid-turbinate nasal swabs. All swabs collected at home should be stored immediately between 2°C and 8°C (in the refrigerator) and brought to the site at the latest at the Day 3, Day 8, and Day 14 visit.

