1. INTRODUCTION

Respiratory syncytial virus (RSV) is considered the most important virus causing acute lower respiratory tract infection (LRTI) and is a major cause of hospital admissions and death in young children worldwide.^{18,22} In addition, LRTI results in substantial illness and morbidity in the elderly and adults with underlying chronic illnesses, underlying disorders of cellular immunity, or suppressed immune systems in hospitalized and community-based patients.^{4,10,11,12,18,19,27} Prospective surveillance from 1975-1995 in 2,960 subjects 18-60 years of age identified 211 RSV infections (7%) by culture. The infections were symptomatic in 84% of subjects, involved only the upper respiratory tract in 74%, and included lower respiratory tract symptoms in 26%. Thirty-eight percent of the patients missed work and they were ill for mean of 9.5 days.¹³

Despite the large medical and economic burden, treatment options for RSV-associated bronchiolitis and pneumonia are limited: prophylactic treatment with passive immunization with the humanized monoclonal antibody palivizumab in pediatric patients, treatment with ribavirin, and supportive treatment such as oxygenation and mechanical ventilation are available in hospitalized patients.^{9,26} In an outpatient setting, standard of care is limited to symptomatic treatment of the flu-like manifestations of the disease. There is an unmet medical need for prophylactic (pre- and post-exposure) as well as therapeutic treatment in both children and adults.

Recent studies in pediatric and adult populations have demonstrated that RSV viral load and severity of disease symptoms are closely correlated, and that the window between the onset of clinical symptoms (day 1 and day 3 for influenza and RSV, respectively) and peak viral load (day 2 and day 6 for influenza and RSV, respectively) is considerably longer for RSV than for influenza.^{1,4,7,8} This increases the likelihood that direct antivirals (small-molecules or biologicals) can be viable RSV treatments and achieve high and sustained antiviral responses and improve disease outcome. Aspired treatment effects include reduction of viral shedding, the prevention of acute LRTIs, reduced need for hospitalization, and in case of hospitalization, shortening of stay in the hospital or intensive care unit by decreasing the need for mechanical ventilation, and reduced incidence of mortality.

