2.1.2. Endpoints

Primary Endpoint

To explore the antiviral effect of JNJ-53718678 on RSV, as measured by qRT-PCR assay in mid-turbinate nasal swabs, the following virologic parameters will be assessed:

- AUC from immediately prior to first dose of study drug (baseline) through Day 3, Day 5, Day 8, and Day 14;
- RSV viral load and change from baseline over time;
- Time to undetectable RSV viral load;
- Proportion of subjects with undetectable RSV viral load at each time point throughout the study.

Secondary Endpoints

The secondary endpoints are:

- Safety and tolerability, as assessed by AEs, clinical laboratory testing, ECGs, vital signs, physical examination, throughout the study;
- Clinical course-related endpoints:

- Duration and severity of signs and symptoms of RSV infection assessed through an instrument for patient-reported symptoms (either the Respiratory Infection-Patient Reported Outcomes [RI-PRO] questionnaire or the Respiratory Infection Intensity and Impact Questionnaire [RiiQ] questionnaire) and additional questions about health and functioning;
- Time to resolution of selected RSV symptoms as reported by the subject (through either the RI-PRO or the RiiQ);
- Respiratory rate, heart rate, body temperature, and peripheral capillary oxygen saturation (SpO₂) as measured by the investigator;
- Pharmacokinetic parameters of JNJ-53718678, as determined by population pharmacokinetics (popPK) modelling.

Exploratory Endpoints

Exploratory endpoints include, but are not limited to:

- Antiviral activity and clinical course by stratification factor (time of symptom onset [≤ 3 days vs > 3 days before randomization], severity of key RSV symptoms at screening), presence of comorbidities, baseline RSV viral subtype and genotype;
- The occurrence of complications with onset after treatment initiation that are associated with RSV per investigator assessment:
 - Bacterial superinfections (eg, pneumonia, sinusitis, bronchitis, bacteremia of presumed respiratory origin per investigator assessment);
 - Exacerbations of underlying pulmonary disease (eg, asthma, chronic obstructive pulmonary disease [COPD]);
 - Exacerbations of underlying cardiovascular conditions.
- The need for antibiotics related to complications associated with RSV per investigator assessment;
- Sequence changes (post baseline) in the RSV F-gene, and other regions of the RSV genome (at the request of the protocol virologist), as compared to baseline;
- Medical resource utilization;

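### Day 9-13 swabs are taken only while a subject is symptomatic, so time to undetectable viral load and the Day 9-13 virologic results follow an outcome-dependent schedule that can differ by arm

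*Protocol*

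**What the plan says.** Section 9.2.1 asks for daily swabs from Day 1 to Day 8 in every subject. Then "On Day 8, the investigator will check whether the subject is still symptomatic", and the schedule splits: "For asymptomatic subjects swabbing will be stopped. For subjects still symptomatic, swabbing will be continued daily until the subject becomes asymptomatic". Footnote q of the Time and Events Schedule repeats the rule with its end point: "For subjects still symptomatic, swabbing will be continued daily until the subject becomes asymptomatic or until Day 13 at the latest". After Day 8, status is followed by daily calls and/or review of the electronic diary. No threshold for being symptomatic is given. The schedule then rejoins: "On Day 14 and Day 21, a swab will be collected during the scheduled visit". The text does not say that these two swabs include subjects whose swabbing had stopped, but that is the natural reading.

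Section 2.1.2 lists under the primary endpoint "AUC from immediately prior to first dose of study drug (baseline) through Day 3, Day 5, Day 8, and Day 14", viral load and its change from baseline over time, "Time to undetectable RSV viral load" and "Proportion of subjects with undetectable RSV viral load at each time point throughout the study".

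Section 11.4.1 plans Kaplan-Meier curves for time-to-event data and a repeated-measures model with treatment, strata, visit, treatment-by-visit, baseline log10 viral load and baseline-by-visit. Symptom status is not a term. AUC differences are to come from contrasts of that model.

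**The concern.** Between Day 8 and Day 14, one outcome decides whether another is measured. The drug's effect on clinical course is a secondary objective (section 2.1.1), and the Introduction states that "RSV viral load and severity of disease symptoms are closely correlated". Blinding prevents deliberate differences in swabbing. It does not prevent differences that arise because a treatment shortens symptoms.

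The parameters are exposed to different degrees.

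- **Time to undetectable.** A subject still positive on Day 8 can be recorded as cleared on Day 9, 10 and so on if symptomatic, but not before the Day 14 (±1) visit if symptom-free. Clearance just before Day 9 can thus be recorded five days late.
- **Proportion undetectable and mean viral load on Days 9-13.** Only symptomatic subjects contribute.
- **AUC to Day 14.** It draws on Days 9-13, but the Day 8 and Day 14 swabs anchor it.
- **Not exposed.** AUC to Days 3, 5 and 8, and proportions on Days 1-8, 14 and 21.

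Section 1.3 says the results will guide the choice of dose and endpoints for later studies. An artefact in clearance time could therefore mislead that choice.

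**Working it through.** **The plan's own figures.** Section 11.3 gives 90% half-widths, and they reproduce.

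- One-group AUC: t × 135/√n gives 1.729 × 135/√20 = 52.2 and 1.714 × 135/√24 = 47.2 (stated: 52 and 47).
- Difference in change from baseline: t × 1.85 × √(2/n) gives 1.686 × 1.85 × √(2/20) = 0.986 and 1.679 × 1.85 × √(2/24) = 0.896 (as stated).

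These rest on Day 1-7 and Day 2-3 data, so the swab rule does not touch them. The documents give no figure for Days 9-13, so the size below rests on assumptions.

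**Simulation A: same true clearance in both arms.** Assumed: clearance time normal with mean Day 9 and SD 3; 40% (placebo) vs 60% (active) asymptomatic on Day 8; the rest lose symptoms at 25% per day; symptoms independent of clearance. Swabs follow section 9.2.1.

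Share of subjects truly clearing between Day 8 and Day 13, who are the ones that can be recorded late: Φ(4/3) − Φ(−1/3) = 0.909 − 0.369 = 0.54.

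| Schedule | Median day recorded, 40% vs 60% | Mean day | Recorded undetectable by Day 11 |
|---|---|---|---|
| Daily swabs for all | 9-10 in both | 9.8 vs 9.8 | 75% vs 75% |
| Protocol, symptom loss possible from Day 9 | 11 vs 14 | 10.9 vs 11.1 | 50% vs 46% |
| Protocol, all symptomatic on Day 8 swabbed on Day 9 | 10 vs 12 | 10.7 vs 11.0 | 55% vs 49% |
| Common days only (1-8, 14, 21) | 14 vs 14 | 11.5 vs 11.5 | 37% vs 37% |

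The protocol schedule creates a difference where none exists, and the common schedule removes it. The median moves a lot because the recorded curve is nearly flat around 50%. The mean moves by only 0.2-0.3 days.

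**Simulation B: symptoms tied to clearance.** Assumed: baseline mean 5.3 and SD 1.5 log10; median decline 0.45 log10 per day; values below 1.5 log10 count as undetectable and are set to 0. Viral kinetics are the same in every column; only symptom duration varies. The repeated-measures model was approximated by sequential regressions.

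| Asymptomatic by Day 8 | 22% | 42% | 62% | 76% | Full swabbing |
|---|---|---|---|---|---|
| Median time to undetectable (day) | 9 | 10 | 14 | 14 | 9 |
| Undetectable on Day 10, among those swabbed | 35% | 18% | 5% | 1% | 57% |
| AUC to Day 14, trapezoid | 760 | 770 | 775 | 776 | 755-758 |
| AUC to Day 14, model-based | 725 | 717 | 755 | 794 | 755-758 |

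When symptoms are unrelated to viral load, the Day 10 proportion (56-57%) and model-based AUC (756-761) are essentially unbiased. Time to undetectable still shifts: Day 9, 10, 11 and 14 as 20%, 37%, 57% and 74% are asymptomatic by Day 8.

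For AUC to Day 14 in the linked case, the trapezoid error is 5 to 18 on about 757. The model-based error runs from −41 to +36, so it has no fixed direction.

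**The case against.** The study is a pilot with about 25 subjects per arm, descriptive Kaplan-Meier curves and no formal hypothesis testing (section 2.2). Interval censoring, denominators and the choice of visits commonly belong in a SAP, and section 11.4.1 defers details to one that is not shown. The simulated kinetics and symptom rates are assumptions, and the median result changes with a small change in swab convention. All of this stands, and it argues against treating the point as critical. It does not remove it: the swab schedule is fixed in the protocol, the protocol itself promises proportions at every time point, and no SAP can recover swabs that were never taken. Bias also distorts estimates and 90% intervals in an exploratory trial.

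Three stronger readings are tempting and are not supported.

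- A reader might infer that AUC to Day 14 is badly distorted. Take a subject at 3 log10 on Day 8 who clears on Day 10. A straight line to Day 14 gives 3 × 144/2 = 216 instead of 3 × 48/2 = 72, an excess of 144 log10 copies × hr/mL, which seems to exceed 20% of 490 = 98. But 144 is the error in one chosen subject, while 98 is a group difference for a Day 1-7 AUC. Under Simulation A's inputs, with 3 log10 on Day 8 in all who are still positive and linear decline, the spurious between-arm gap is about 7 to 13.
- A reader might infer that the whole primary endpoint is compromised. AUC to Days 3, 5 and 8 and the proportions on Days 1-8, 14 and 21 keep a common schedule.
- A reader might infer that the active arms will look slower. That follows only if treatment shortens symptoms, which the documents do not show for this population.

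**Conclusion.** The concern holds for time to undetectable viral load and for the proportions and mean viral loads on Days 9-13. It holds weakly, and without a fixed direction, for AUC to Day 14. With identical true clearance and 40% vs 60% asymptomatic on Day 8, the recorded median moves from Day 10-11 to Day 12-14 and the mean by 0.2-0.3 days. These figures show direction and rough size only, because the clearance distribution and symptom rates are assumed. The mechanism for time to undetectable does not need symptoms and viral load to be correlated; it needs only that symptom duration differs by arm. The bias in Day 9-13 proportions does need that correlation, which the protocol asserts. This should be fixed, but it does not threaten the early AUC results or the stated precision.

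**What to change.** Add to section 11.4.1, and carry into the SAP:

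- Between-arm comparisons of time to undetectable, proportion undetectable and viral load use only the swab days common to all subjects (Days 1-8, 14 and 21).
- Clearance between Day 8 and Day 14 is treated as interval-censored.
- Arms are not compared on Days 9-13. Those swabs are listed, or used only in a labelled sensitivity analysis.
- AUC to Day 14 is reported from the common days, with an all-swab version as sensitivity.

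State also in section 9.2.1 that the Day 14 and Day 21 swabs are taken from every subject.

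The cost is a few sentences and no extra visits. Clearance between Days 8 and 14 is timed more coarsely, and AUC to Day 14 relies on interpolation over those six days for every subject, equally across arms. If daily resolution matters more, the alternative is the same Day 9-13 schedule for all subjects regardless of symptoms, at the price of more swabs.
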